### 11.2.3. Relationship to Study Drug

Relationship should be assessed and provided for every adverse event/serious adverse event based on currently available information. Relationship is to be reassessed and provided as additional information becomes available. Adverse events will be classified by the Investigator as follows:

### **Related for Regulatory Reporting Assessment:**

• **Definitely Related**: There is clear evidence to suggest a causal relationship, and other possible contributing factors can be ruled out. The clinical event, including an abnormal laboratory test result, occurs in a plausible time relationship to drug administration and cannot be explained by concurrent disease or other drugs or chemicals. The event resolves or improves upon withdrawal of drug (de-challenge). The event would be considered as definitely related to the study drug upon results of a positive re-challenge procedure.

- **Probably Related**: There is evidence to suggest a causal relationship (e.g., the event occurred within a reasonable time after administration of the trial medication). However, the influence of other factors that may have contributed to the event (e.g., the patient's clinical condition, other concurrent disease, concomitant medications or events) is unlikely, and the event follows a clinically reasonable response upon withdrawal of drug (de-challenge).
- **Possibly Related:** There is evidence to suggest a causal relationship (e.g., the event occurred within a reasonable time after administration of the study drug). However, the influence of other factors may have contributed to the event (e.g., the patient's clinical condition, other concurrent disease, concomitant medications or events).

### **Unrelated for Regulatory Reporting Assessment:**

- Unlikely Related: A clinical event, including an abnormal laboratory test result, whose temporal relationship to drug administration makes a causal relationship improbable (e.g., the event did not occur within a reasonable time after administration of the trial medication) and in which other drugs or concurrent or underlying disease provide plausible explanations (e.g., the patient's clinical condition, other concomitant treatments).
- **Not related**: The adverse event is completely independent of study drug administration, and/or evidence exists that the event is definitely related to another etiology. There must be an alternative, definitive etiology documented by the clinician.

#### 11.2.4. Duration

For all adverse events whether or not considered serious, the Investigator will provide a record of the start and stop dates of the event. Every effort should be made to resolve all adverse events with continued follow-up with the patient until appropriate resolution can be achieved. If an event is unresolved at the end of the study it will be recorded as ongoing.

#### 11.2.5. Action Taken

The Investigator will record the action taken with investigational product as a result of an adverse event or serious adverse event on the eCRF, as applicable (e.g., discontinuation, or interruption of investigational product, as appropriate) and record if concomitant and/or additional treatments were given for the event.

#### **11.2.6. Outcome**

The Investigator will record the outcome of adverse events on the eCRF, as applicable (e.g., recovered, recovered with sequelae, not recovered, or death (due to the adverse event).

## 11.3. Follow-Up

Adverse events, severe adverse events and serious adverse events, including clinically significant laboratory tests, electrocardiograms, or physical examination findings, will be followed, regardless of causality, for as long as necessary to adequately evaluate the patient's safety, or until the event stabilizes, is otherwise explained, death occurs, or the patient is lost to follow up. If resolved, a resolution date should be provided. The Investigator is responsible for ensuring

that follow-up includes any supplemental investigations indicated to elucidate the nature and/or causality of the adverse event. This may include additional clinical laboratory testing or investigations, examinations, or consultation with other health care professionals as is practical.

## 11.4. Pregnancy

The Sponsor must be informed within 24 hours upon learning that a patient, or male patient's partner, has become pregnant any time after the first dose of study drug until 30 days after the last dose of study drug. The Pregnancy Notification eCRF in EDC should be used to report the pregnancy to the Sponsor or its designee. Patient pregnancies (or pregnancy of a male patient's partner) must be followed until termination of pregnancy or the birth of the child. The Pregnancy Outcome eCRF should be used to report information regarding the status of the infant.

If pregnancy occurs in a female patient, then study drug should be discontinued immediately. While pregnancy itself is not considered to be an AE or SAE, any pregnancy complication should be reported as an adverse event or serious adverse event if reporting criteria are met. Spontaneous abortion, and any congenital anomaly or birth defect in the patient's (or male patient's partner's) newborn should be reported as an SAE.

If a female partner of a male patient taking investigational product becomes pregnant, the male patient taking the investigational product should notify the Investigator, and the pregnant female partner should be advised to call her healthcare provider immediately.

## 11.5. Recording Adverse Events

All adverse events (regardless of seriousness or relationship to study drug) including those from the time informed consent is obtained through to the final study visit are to be recorded in the eCRF. Each individual adverse event is to be listed as a separate entry. The Investigator will provide information about dates of onset and resolution, seriousness, severity, action(s) taken, outcome, and relationship to the study drug. All adverse events should be documented in the patient's source documents.

## 11.6. Reporting Adverse Events

The Investigator must report to Sponsor or its designee all adverse events that occur during the study from the time written informed consent is given until the final study visit or early termination, regardless of their relationship to the study drug. Serious adverse events and pregnancies will be reported from the time written informed consent is given through completion of the safety follow-up visit, as applicable.

#### 11.6.1. Reporting Serious Adverse Events

The Investigator is required to notify the Sponsor, and the Sponsor's designated Drug Safety Unit within 24 hours after becoming aware of the occurrence of a serious adverse event. All serious adverse events will be reported through completion of the adverse event eCRF. The Investigator will be responsible for reporting serious adverse events to the IRB/EC.

United States and Canada and Emergency Contact Information:

| , MD       |     |
|------------|-----|
| Telephone: |     |
| Facsimile: |     |
| Email:     | AND |

#### 11.6.2. Reporting Urgent Safety Issues

If the study site staff becomes aware of an actual or potential urgent safety issue, then the Sponsor and Sponsor's designee [Medical Monitor(s)] must be immediately contacted so that appropriate urgent safety measures can be agreed upon. An urgent safety issue is defined as:

- An immediate hazard to the health or safety of patients participating in a clinical study
- A serious risk to human health or potentially a serious risk to human health

An urgent safety issue may include: (1) issues with an investigational drug or comparators; (2) study procedures; (3) inter-current illness (including pandemic infections); (4) concomitant medications; (5) concurrent medical conditions; or (6) any other issues related to the safe conduct of the study or that pose a risk to study patients.

In exceptional circumstances of imminent hazard and in order to safeguard the health or safety of individuals, the Investigators may take urgent safety measures before informing the Sponsor, but the Sponsor must be informed immediately after the hazard has resolved.

#### 12. STATISTICAL METHODS

## **12.1.** Sample Size Rationale

Power is calculated for the Primary Efficacy Endpoint for the continuity-corrected chi-square test using a 2-sided significance level of 0.025. Based on Phase 2 results, the percentage of patients achieving an absolute SALT score ≤20 at Week 24 is assumed to be 40%, 26%, and 9% for the CTP-543 12 mg, CTP-543 8 mg BID, and placebo groups, respectively. Patients will be randomized in a 1:2:1 ratio with a total N of approximately 440 patients (i.e., 110 for 12 mg BID, 220 for 8 mg BID, and 110 for placebo BID). These sample sizes will provide >99% power for the comparison of CTP-543 12 mg BID versus placebo and approximately 92% power for the comparison of CTP-543 8 mg BID versus placebo.

## 12.2. Endpoints

#### **12.2.1.** Efficacy

### **Primary Efficacy Endpoint**

• The primary efficacy endpoint will be the percentage of patients achieving an absolute SALT score of ≤20 at Week 24.

### **Key Secondary Endpoints**

- 1. Percentage of responders (defined as "satisfied" or "very satisfied") on the Hair Satisfaction Patient Reported Outcome (SPRO) scale at Week 24
- 2. Percentage of patients achieving an absolute SALT score of ≤20 at Week 20, 16, 12 and 8

See Section 12.4.3 for details on multiple comparisons control for Primary and Key Secondary Endpoints.

#### **Secondary Endpoints**

- Relative change in SALT scores from Baseline at Weeks 4, 8, 12, 16, 20, and 24
- Percentage of responders (defined as "much improved" or "very much improved") using the CGI-I at Weeks 12, 16, 20, and 24
- Percentage of responders (defined as "much improved" or "very much improved") using the PGI-I at Weeks 12, 16, 20, and 24
- Change from Baseline in the CGI-S at Weeks 12, 16, 20, and 24
- Change from Baseline in the PGI-S at Weeks 12, 16, 20, and 24
- Percentage of patients achieving at least a 75% relative reduction in SALT score from Baseline at Weeks 12 and 24
- Percentage of patients achieving at least a 90% relative reduction in SALT score from Baseline at Weeks 12 and 24

- Change from Baseline on the Brigham Eyebrow Tool for Alopecia (BETA) score at Weeks 12 and 24
- Change from Baseline on the Brigham Eyelash Tool for Alopecia (BELA) score at Weeks 12 and 24
- Percentage of responders (defined as "satisfied" or "very satisfied") on the SPRO scale at Weeks 12, 16, and 20
- Change from Baseline in the SPRO scale at Weeks 12, 16, 20 and 24
- Percentage of patients achieving a ≥ 2-point change from Baseline in the SPRO scale at Weeks 12, 16, 20, and 24
- Change from Baseline on the individual items of the Hair Quality Patient Reported Outcome (QPRO) scale at Weeks 12, 16, 20 and 24
- Change from Baseline in the depression scale of the Hospital Anxiety and Depression Scale (HADS) at Week 24
- Change from Baseline in the anxiety scale of the Hospital Anxiety and Depression Scale (HADS) at Week 24
- Percentage of patients achieving an absolute SALT score of ≤20 at Weeks 8 and 4
- Percentage of patients achieving an absolute SALT score of ≤10 at Week 24

Additional exploratory statistical analyses to further assess for treatment effect will be outlined in the Statistical Analysis Plan finalized prior to database lock for the Primary Efficacy Analysis

### **12.2.2.** Safety

Safety and tolerability of CTP-543 will be assessed by evaluating adverse events, vital signs, concomitant medications, and clinical laboratory results, as well as physical examinations.

#### 12.2.3. Pharmacokinetic

CTP-543 population PK analysis will be conducted using sparse PK samples in a subset of patients. Pharmacokinetic samples will be collected per the schedule of assessments (Table 2).

## 12.3. Analysis Populations

#### 12.3.1. Treatment Period

The Efficacy Population will include all patients who are randomized in the study and dispensed study drug during the Treatment Period.

The Pharmacokinetic Population will include all patients who receive study drug and have at least 1 pharmacokinetic sample taken during the Treatment Period. Patients who receive placebo will be excluded from the Pharmacokinetic Population.

The Safety Population will include all patients who receive study drug during the Treatment Period.

The Per Protocol Population will include all patients in the Efficacy Population who were dosed according to protocol and have no major protocol deviations. Inclusion in the Per Protocol Population will be determined prior to breaking the study blind.

In the event patients incorrectly receive treatment associated with a different treatment group, they will be analyzed "as randomized" for efficacy and "as treated" for safety.

## 12.4. Analyses

For the Treatment Period, data will be summarized by active treatment versus placebo-treated patients (i.e., by treatment group). All data for analysis will be listed by patient.

Continuous measures will be summarized descriptively (mean, standard deviation, median, minimum value, and maximum value) and categorical measures will be presented as number and percentage.

Additional details for statistical methods will be provided in the Statistical Analysis Plan.

#### 12.4.1. Disposition and Baseline Characteristics

Disposition will be summarized by randomized treatment group. The number and percentage of patients, who are randomized, treated, prematurely discontinued, (overall and by reason for discontinuation), and complete the study will be summarized.

Baseline characteristics will be summarized by treatment group.

The number of patients in each treatment group will be summarized for each investigative site for the Treatment Period. Medical history will be coded with the Medical Dictionary for Regulatory Activities (MedDRA) terminology and summarized by system organ class and preferred term. Prior and concomitant medications will be summarized separately by World Health Organization Drug Dictionary Anatomical-Therapeutic-Chemical classification and preferred term.

#### **12.4.2.** Efficacy

The primary analysis targets an effect of treatment (response rates at 24 weeks) among subjects given the opportunity for treatment who are dispensed study drug. The treatment policy strategy is used for the intercurrent event of discontinuation of study treatment (either temporarily or permanently) and so the response rates at 24 weeks are of interest, irrespective of continued therapy, in line with the intent-to-treat principle.

For the primary efficacy analysis and the key secondary efficacy analysis, a 0.025 (two-sided) alpha-level will be allocated to each dose for comparison with placebo to adjust for multiplicity of testing associated with two doses. Additional secondary endpoints will be tested in the following order (see Section 12.4.3) and be considered statistically significant and alpha-level protected if they (and all prior endpoints in the hierarchy for that dose versus placebo) achieve statistical significance at the 0.025 level of significance. Irrespective, nominal p-values will be provided. Testing will be performed only for the Treatment Period. Missing values will be handled as specified in Section 12.4.4.

## **Primary Efficacy Endpoint**

The primary efficacy endpoint will be the proportion of patients achieving an absolute SALT score  $\leq 20$  at Week 24. Pairwise treatment group differences from placebo will be assessed with the Cochran-Mantel-Haenszel test using baseline scalp hair loss (partial vs complete/near-complete) as the stratification factor, for each active treatment group versus placebo.

[figure not shown]
#### **Other Efficacy Endpoints**

For proportions of patients achieving specified improvement criteria (eg, CGI-I and PGI-I responders), pairwise treatment group differences from placebo at each scheduled evaluation will be assessed with the Cochran-Mantel-Haenszel test using baseline scalp hair loss as the stratification factor.

Absolute and/or relative changes in SALT score, SPRO score, CGI-S and PGI-S values, BELA and BETA score, QPRO scores, and HADS anxiety and depression scores, will be assessed with a mixed effects repeated measures (MMRM) model. The model will include fixed factors for treatment group, study visit, and treatment by study visit interaction, with baseline SALT score as a covariate. Treatment group comparisons at each visit will be based on least squares mean estimates. An unstructured covariance structure will be used to model the within-subject errors. The Kenward-Roger approximation will be used to estimate denominator degrees of freedom.

#### 12.4.3. Multiplicity

Hierarchical testing will be used to control for multiple comparisons. For the primary efficacy analysis and the key secondary efficacy analyses, a  $\leq 0.025$  (two-sided) alpha-level will be allocated to each dose for comparison with placebo to adjust for multiplicity of testing associated with two doses. The below figure displays the order of testing of the key secondary endpoints. Once p>0.025 is observed for a treatment group comparison, inference for additional endpoints is no longer alpha-level protected for that dose group, however nominal p-values will still be reported.

#### 12.4.4. Missing Data for SALT-based endpoints

Prior to database lock, the classification of the missing data pattern for missing SALT scores will be finalized based on blinded data review and documented as either considered to be missing at random (MAR) or potentially missing not at random (MNAR), consistent with general categories of reasons for missingness. Subjects with missing data due to COVID-19 will have data reviewed to determine the specific limitation imposed by COVID-19 leading to the inability to have captured the protocol-specified assessments. For example, missing at random will be considered plausible for COVID-19 related reasons such as site closures and travel limitations. In general, however, if a MAR assumption is not considered plausible, MNAR will be assumed. Patterns of missing values across visits will be listed and summarized with numbers and percentages by treatment and visit.

### **12.4.5.** Multiple Imputation

A multiple imputation (MI) approach will be used to estimate missing SALT scores. Analyses of the multiply imputed datasets will be performed for both the primary endpoint (percentage of subjects with absolute SALT scores  $\leq 20$ ) as well as key secondary endpoints employing SALT scores, between each dose and placebo, using the MMRM approach.

The imputation will be implemented separately for each treatment, under the assumption that different treatments may have distinct posterior distributions. Missing values will be imputed with a sequential regression approach under the assumption of multivariate normality. Missing SALT scores will be imputed in a sequential manner using regression models with a number of predictor variables. Covariates to be included are the baseline SALT score, in addition to the observed or imputed values of the previous time points.

One hundred independent imputations will be done with SAS® PROC MI using the Fully Conditional Specification (FCS) regression method for all imputed continuous variables and the discriminant function method for all imputed classification variables, if needed. For each continuous variable, all other variables are used as covariates, and for each imputed classification variable, all other continuous variables are used as covariates. The FCS method combines both the monotone and arbitrary missing data patterns into one procedure.

## 12.4.5.1. Analysis of Imputed Datasets

For the analysis of the primary endpoint (i.e., the binary endpoint denoting a SALT score  $\leq$  20) the individual SALT scores will be categorized ( $\leq$  20 versus > 20) and analyzed using a Mantel-Haenszel test (comparing each dose to placebo, separately). For each imputed dataset, treatment differences will be assessed using the Mantel-Haenszel estimate of a common risk difference, with the variance estimator due to Sato (used to construct confidence limits for the Mantel-Haenszel estimate of the common risk difference in the SAS FREQ Procedure). The resulting 100 estimates of the treatment differences and standard errors will then be combined using SAS PROC MIANALYZE.

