#### 6.2. Demographic and Other Baseline Characteristics

Demographic characteristics (ie, sex, ethnic origin, race, age, and calculated body mass index) will be collected at the Screening Visit, between Day -28 and -1, and detailed on the eCRF. Demographic characteristics will be summarized using descriptive statistics for all randomized patients by treatment group and overall.

Baseline characteristics will be summarized using descriptive statistics for all randomized patients by treatment group and overall and will include the following:

- baseline total SALT score
- Alopecia areata classification (randomization strata via IWRS): partial scalp hair loss  $(SALT \ge 50 \text{ and } < 95)$ ; complete or near-complete scalp hair loss  $(SALT \ge 95)$
- duration of current episode in years (calculated as: [date of randomization date of current episode onset + 1] / 365.25)
- current nail involvement: yes; no (collected via eCOA system as 'HAND IMAGE CAPTURE')
- nasal hair involvement: yes; no (collected on the Physical Examinations eCRF page)
- eyebrow involvement: yes; no (collected as part of the BETA assessment)

- eyelash involvement: yes; no (collected as part of the BELA assessment)
- whether the patient has experienced any past and/or concomitant diseases, conditions, or exposures to serious infections such as HIV, or past surgeries: yes; no (collected via the Medical History Summary eCRF page)

Other co-morbidities may be identified and included as baseline characteristics.

All demographics and baseline characteristics will also be listed within a by-patient data listing for all randomized patients.

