#### 8.2.1. Computation of the Primary Endpoint

The SALT is a measure of hair loss that quantifies the amount of scalp surface without hair in a pre-specified quadrant of the scalp (right side, top, left side, back), that is further summed after applying a quadrant-specific multiplier indicative of scalp surface area contribution, to provide an overall score of total hair loss. A total SALT score equal to 0% indicates complete hair growth. A total SALT score equal to 100% indicates complete hair loss. An example of the SALT assessment can be found in Appendix 17.2 of protocol. The overall total SALT score is calculated in the eCOA system and will not re-derived. SALT scores are considered missing if the overall total could not be calculated. The primary endpoint is derived by categorizing the individual overall SALT scores at Week 24 ( $\leq 20$  versus > 20).

A multiple imputation (MI) approach will be used to estimate missing SALT scores.

One hundred independent imputations will be done with SAS® PROC MI using the Fully Conditional Specification (FCS) regression method. The FCS method combines both the monotone and arbitrary missing data patterns into one procedure, imputing missing values with a sequential regression approach.

For the primary efficacy analysis, missing SALT scores will be imputed under a missing at random (MAR) assumption. This assumes that patients who have missing data would have similar SALT scores as other patients in their respective treatment arm who have complete data. Any missing post-baseline SALT scores will be imputed to better inform the estimates of Week 24 missing SALT scores. Patients who have discontinued treatment but remain on study will not have their SALT scores censored, but any arbitrary missing SALT scores after the patient discontinued treatment will be imputed in the same manner. Utilizing the FCS method, missing

SALT scores will be imputed in a sequential manner using regression models with baseline SALT score and the observed or imputed values of previous visits as covariates. Imputations will be implemented separately for each treatment under the assumption that different treatments may have distinct posterior distributions.

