#### 8.2.2. Primary Analysis of the Primary Endpoint

Pairwise treatment group differences from placebo will be assessed with the Mantel-Haenszel test (common risk difference) using baseline scalp hair loss (partial vs complete/near-complete) as the stratification factor, for each active treatment group versus placebo.

For each imputed dataset, treatment differences will be assessed using the Mantel-Haenszel estimate of a common risk difference, with the variance estimator (used to construct confidence limits for the Mantel-Haenszel estimate of the common risk difference in the SAS FREQ Procedure). The resulting 100 estimates of the treatment differences and standard errors will then be combined using SAS PROC MIANALYZE. The following SAS options for PROC FREQ will be used to estimate a common risk difference, confidence intervals, and p-values by imputation for placebo compared to each dose separately:

proc freq data = <>;
by IMPUTATION;
tables STRATA\*TREATMENT\*RESPONSE / commonriskdiff(cl=mh test=mh);
run;

The observed number and percentage of patients with an absolute SALT score  $\leq 20$  among nonimputed data will be reported by treatment group along with the appropriate p-value, the combined treatment differences, combined standard errors, and 95% confidence intervals (CI). This analysis will be completed for the Efficacy Population and the Per Protocol Population. The analysis utilizing the Per Protocol Population is considered supportive. The results may also be displayed graphically.

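### The primary responder test is valid but leaves out continuous baseline SALT, which is already collected and modelled elsewhere, and so forgoes a modest gain in precision for the 8 mg comparison

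*Protocol*

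**What the plan says.** Protocol 12.4.5.1 states that in each imputed dataset "treatment differences will be assessed using the Mantel-Haenszel estimate of a common risk difference, with the variance estimator due to Sato". SAP 8.2.2 uses the same common risk difference, without naming Sato, and gives the adjustment: "using baseline scalp hair loss (partial vs complete/near-complete) as the stratification factor, for each active treatment group versus placebo". Those two classes are also the randomisation strata (Protocol 7.3).

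Continuous baseline SALT is used elsewhere. SAP 8.2.1 imputes missing SALT scores "using regression models with baseline SALT score and the observed or imputed values of previous visits as covariates". SAP 8.4.1 to 8.4.10 put baseline SALT in every MMRM and in the HADS ANCOVA. SAP 6.2 lists it as a baseline characteristic, along with "duration of current episode in years", which enters no model.

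No planned analysis of the primary endpoint adjusts for more than the two strata. The MNAR and Modified Efficacy Population analyses in SAP 8.2.3 repeat the 8.2.2 test, the tipping-point analysis shifts imputed values without adding a covariate, SAP 8.2.4 specifies no secondary analysis, and SAP 8.6 plans no subgroups.

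**The concern.** The endpoint is an absolute score, so the distance to response depends on the starting score. The partial stratum covers SALT 50 to just under 95 and holds nearly all of that gradient. The stratified test makes no distinction among patients within it. If starting SALT predicts response within the stratum, the variation it explains stays in the standard error of the primary risk difference.

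Efficiency is what is at stake, mainly for 8 mg, which has the lower planned power and must pass at 0.025 before its key secondary endpoints can be tested with alpha protection (SAP 8.1.4).

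**Working it through.** **1. Required reduction.** From baseline B, reaching SALT 20 needs a relative reduction of 1 − 20/B:
- B = 50: 60%
- B = 75: 73%
- B = 95: 79%
- B = 100: 80%

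Across the partial stratum the range is 60% to 79%. In the complete/near-complete stratum it is only 79% to 80%.

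**2. Planned power.** Protocol 12.1: "Power is calculated for the Primary Efficacy Endpoint for the continuity-corrected chi-square test", "using a 2-sided significance level of 0.025". The response rate "is assumed to be 40%, 26%, and 9% for the CTP-543 12 mg, CTP-543 8 mg BID, and placebo groups, respectively", with "110 for 12 mg BID, 220 for 8 mg BID, and 110 for placebo BID". The formula is

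power = Φ{[d − ½(1/n₁ + 1/n₂) − z·SE₀] / SE₁}, with z = 2.241 for two-sided 0.025.

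- 8 mg versus placebo: d = 0.17. The pooled rate is (57.2 + 9.9)/330 = 0.2033, so SE₀ = √[0.2033 × 0.7967 × (1/220 + 1/110)] = 0.0470. SE₁ = √(0.26 × 0.74/220 + 0.09 × 0.91/110) = 0.0402. The continuity term is 0.0068. Power = Φ[(0.17 − 0.0068 − 0.1053)/0.0402] = Φ(1.437) = 92.5%, against about 92% stated.
- 12 mg versus placebo: d = 0.31, SE₀ = 0.0580, SE₁ = 0.0541, continuity term 0.0091. Power = 99.92%, against >99% stated.

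Both stated figures reproduce, and neither relies on any covariate adjustment.

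**3. Variance that baseline SALT could remove.** The documents do not say how strongly SALT predicts response within stratum. Assumptions: 40 to 55% of patients have SALT ≥95; baseline SALT is uniform on 50 to 95 otherwise; the log-odds of response fall linearly with baseline SALT; marginal rates stay at 26% and 9%. Large-sample variance of the 8 mg risk difference, two strata divided by adjustment for SALT as well:

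| Fall in log-odds per 10 SALT points | Variance ratio |
|---|---|
| 0.15 | 1.00 |
| 0.3 | 1.01–1.02 |
| 0.5 | 1.04–1.05 |

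A ratio of 1.05 is a reduction of 1 − 1/1.05 = 4.8%, equivalent to about 330 × 0.048 ≈ 16 of the 330 patients in this comparison.

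In simulations of 2,000 trials per scenario where neither SALT nor episode duration was prognostic, adjusting for both raised the variance by 0.5 to 0.6% for 8 mg and 1.0 to 1.2% for 12 mg. That is the cost if the covariates carry no information.

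**4. Effect on power.** Putting n/(1 − reduction) into the formula of step 2:

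| Variance reduction | 8 mg power | 12 mg power |
|---|---|---|
| 0% | 92.5% | 99.92% |
| 1% | 92.8% | 99.93% |
| 3% | 93.4% | 99.94% |
| 5% | 94.0% | 99.95% |

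**5. Chance imbalance.** A uniform 50–95 distribution has SD 45/√12 = 13.0. With 60% of patients partial (132 versus 66), a two-SE imbalance in mean SALT is 2 × 13.0 × √(1/132 + 1/66) = 3.9 points. With 45% partial (99 versus 49.5) it is 4.5 points. Under the slopes in step 3 this moves the overall risk difference by 0.4 to 1.7 percentage points, or 0.1 to 0.4 of the 4.0-point standard error.

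**6. Validity.** In null simulations (4,000 trials per scenario, Monte Carlo SE about 0.25 points), rejection at nominal 2.5% was 2.6 to 3.1% for the planned test and 2.6 to 3.2% for an estimator adjusted for SALT and duration.

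**The case against.** The strongest reply is that this is a preference about efficiency. The test is pre-specified, matches the randomisation strata and meets the stated power without further adjustment. The gain depends on a slope that the documents do not give, and the required-reduction arithmetic does not supply that slope. All of this stands, and it limits the point to an optional improvement.

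Four stronger readings are tempting, and the documents do not support them.

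- A reader might infer that the test is biased or unprotected against imbalance. Randomisation and test share the severity factor, which deals with imbalance between the two classes. The remaining within-stratum imbalance is random variation that the planned confidence interval already covers, and step 6 shows no gain in error control from adjusting.
- A reader might infer that the primary test is an anomaly in the plan. Every responder test omits continuous SALT (Protocol 12.4.2; SAP 8.3 and 8.4). The plan is consistent: stratified tests for binary endpoints, covariate models for continuous ones.
- A reader might infer that baseline SALT plays no part in the primary analysis. It is in the imputation model, so only the test omits it.
- A reader might count episode duration as a further loss. Variance reductions of 9 to 11%, with 8 mg power near 95.3%, appear only if strong effects are assumed for both SALT (odds ratio 0.55 per 10 points) and duration (0.82 per year). The documents give no evidence that duration predicts response, and it is not in the imputation model.

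**Conclusion.** The planned Mantel-Haenszel test is valid, and the stated power reproduces. Like every other responder test in the plan, it forgoes a modest gain: about 0 to 5% of the variance of the 8 mg versus placebo risk difference, or up to about 1.5 power points (92.5% to 94.0%). For 12 mg the effect on power is negligible. If baseline SALT is not prognostic within stratum, adjusting for it costs about 1% of variance.

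These sizes rest on the assumed share of patients with SALT ≥95, a uniform SALT distribution in the partial stratum and the assumed slopes. The plan's own use of baseline SALT as a covariate makes some prognostic value plausible but does not quantify it. The change is worth making because it is cheap and keeps the marginal risk difference as the estimand. It is not the correction of an error.

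**What to change.** In SAP 8.2.2, for the Week 24 primary endpoint only:

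1. In each imputed dataset, fit a logistic model with treatment, randomisation stratum and continuous baseline SALT. Average the predicted probabilities under each treatment, take the difference with a robust standard error, and combine with PROC MIANALYZE as planned. At the assumed rates about 67 responders (57.2 + 9.9) are expected for 8 mg versus placebo and 54 (44 + 9.9) for 12 mg versus placebo, which is adequate for three terms.
2. Keep the two-stratum Mantel-Haenszel result as a sensitivity analysis.
3. Name the estimator for each alpha-controlled test in advance, for example Mantel-Haenszel for SALT ≤20 at Weeks 20, 16, 12 and 8. A fallback triggered by the number of responders would let the data choose the estimator inside the hierarchy. SAP 8.3.1, 8.3.2 and 8.4 refer back to 8.2.2, so those cross-references must say which estimator they mean, including for SPRO at Week 24.
4. Leave episode duration out unless it is also added to the imputation model.
5. Record the change in SAP 13.

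The cost is SAP wording and a short program before unblinding, with no new data. The downside is a model-based estimator that brings little or no gain if baseline SALT is weakly prognostic. If the sponsor prefers to leave the primary test alone, the same model can be pre-specified as a supportive analysis in SAP 8.2.4, which is now empty.
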